**Table 1: Subgroup Analyses for Efficacy and Safety Endpoints**

Subgroup	Definition	Analysis Type
Sex	Male, Female	E, S
Age	E: <75, ≥75 years S: < 65, 65 to < 75, and ≥ 75 years	E, S
Race	White, Other	E, S
Region	Asia/Pacific, Other	E, S
Baseline weight	≤ 65 kg, >65 to 85 kg, and >85 kg	E, S
Baseline renal function (Glomerular filtration rate [GFR] [mL/min/1.73m  ])	E: ≤60, >60 (mL/min/1.73m  ) S: <30, 30 to <60, 60 to <90, and ≥90 (mL/min/1.73m  )	E, S
Baseline hepatic function	Normal, Impaired a	S
ISS staging	I, II, and III	E
Number of prior lines of therapy	≤ 4 lines, >4 lines	E
Type of myeloma	IgG, non-IgG	E
Cytogenetic risk	High risk, Standard risk	E
ECOG performance score	0, ≥1	E
E: efficacy (ORR); S: safety (TEAEs).		
a Includes mild, moderate and severe.		

## 3. INTERIM ANALYSIS AND DATA MONITORING COMMITTEE REVIEW

No interim analysis is planned for this study.

An independent Data Monitoring Committee (DMC), consisting of 2 clinicians and 1 statistician, will be established to review safety data periodically during the study. The DMC will review comprehensive safety data and provide recommendations concerning the conduct of the study. The details will be provided in a separate DMC charter.

The statistical analysis plan for the DMC will be provided in a separate DMC SAP.

## 4. SUBJECT AND TREATMENT INFORMATION

Analyses of subject disposition, demographic and baseline disease characteristics will be conducted on ITT analysis set. Analyses on extent of exposure will be conducted on safety analysis set. No statistical comparisons between the two treatment groups will be performed.

#### 4.1. Subject Disposition

The number of subjects who are randomized, treated, ongoing, and discontinued treatment with reasons of discontinuation reported on eCRF will be summarized. The number of subjects who discontinued from study with the reported reasons will also be presented. The number of subjects who discontinued treatment by cycle with the reported reasons will also be provided.

Subject enrollment will also be summarized by country and site for intent-to-treat analysis set.

A listing of subjects who discontinued treatment with study drug including reasons for discontinuation will be provided. A similar listing will be provided for subjects who discontinued study.

#### 4.2. Demographics and Baseline Characteristics

The following subject demographics will be summarized using descriptive statistics:

- Age (continuous)
- Age category (< 65 years, 65 to < 75 years, and  $\geq$  75 years)
- Sex (male, female)
- Race (White, Black or African American, Asian, American Indian or Alaska Native, Native Hawaiian or other Pacific Islander, and Not reported)
- Ethnicity (Hispanic or Latino, Not Hispanic or Latino)
- Height (cm)
- Weight (kg) ( $\leq$ 65 kg, >65 kg to 85 kg, >85 kg)
- Baseline ECOG performance status (0, 1, 2)

The following baseline disease characteristics will be summarized using descriptive statistics:

- Type of myeloma (IgA, IgD, IgE, IgG, IgM, light chain, biclonal, or negative immunofixation)
- Type of measurable disease (serum and urine, serum, urine, FLC)
- ISS staging (I, II, III)
- standard-risk and high-risk cytogenetic abnormalities (del17p, t(4;14), t(14;16))
- Time since initial diagnosis to randomization (years)
- Number of lytic bone lesions (None, 1-3, 4-10, more than 10)
- Presence of diffuse myeloma-related osteopenia (Yes, No)
- Presence of extramedullary plasmacytomas (Yes, No)
- Bone marrow % plasma cells (<10, 10 – 30, > 30)

In addition, a descriptive summary of selected hematology and chemistry laboratory analytes at baseline will be provided for each treatment group and overall. The baseline toxicity grade of selected laboratory analyte in hematology and chemistry panel will be summarized by treatment group using frequency.

In addition, a summary of stratification factors used in the randomization (body weight at baseline, number of prior lines of therapy, and type of myeloma) based on IWRS will be provided to evaluate whether or not randomization process was appropriately executed in the study.

### **4.3. Medical History**

General medical history will be summarized by body system organ class and preferred term for each treatment group and overall.

### **4.4. Prior Therapies**

#### **4.4.1. Prior Multiple Myeloma Therapies**

The number and percentage of subjects who had prior exposure to multiple myeloma therapies (systemic therapy, autologous stem cell transplant [ASCT], radiotherapy, cancer-related surgery) will be summarized by treatment group. Specifically, for prior systemic therapies, the number of prior lines of therapy will be summarized descriptively and summarized by the following categories:  $\leq 4$  and  $> 4$ .

The summary of prior systemic therapies will be presented by therapy class and therapy. The therapy classes include proteasome inhibitors (PI), immunomodulatory drugs (IMiD), steroids, alkylating agents and anthracyclines.

- PI therapy class includes: bortezomib, carfilzomib, oprozomib, ixazomib, and marizomib;
- IMiD therapy class includes: lenalidomide, pomalidomide, and thalidomide;
- Steroids therapy class includes: dexamethasone and prednisone, among others.

Further update of the above lists will be specified in the Data Presentation Specifications (DPS). The number of subjects who had prior exposure to multiple therapy classes (e.g., PI + IMiD) or multiple therapies (e.g., bortezomib + lenalidomide) may be provided, if the number of subjects who exposed to those therapy class or therapies is sufficient.

Additionally, the prior systemic therapy will be summarized by therapeutic class, pharmacologic class and preferred term.

#### **4.4.2. Refractory Status to Prior Systemic Therapy**

Refractory status (yes, no) to a particular prior systemic therapy class (i.e., PI/IMiD) or prior systemic therapy (e.g., bortezomib or thalidomide) will be based on refractory status to each line of therapy, or each specific therapy collected on prior systemic therapy CRF page. For each subject, refractory to each therapy class/therapy refers to refractory to his/her most recent therapy-containing line.

The number and percentage of subjects' refractory status to the most recent PI or IMiD therapy class will be summarized by the following 4 categories: none (neither PI-refractory nor IMiD-

refractory), PI only (PI-refractory but not IMiD-refractory), IMiD only (IMiD-refractory only but not PI-refractory), both PI and IMiD. Refractory to specific prior therapy, such as bortezomib, carfilzomib, ixazomib, lenalidomide, pomalidomide, or thalidomide and the relevant combinations of the aforementioned therapies will be provided separately.

The incidence of subjects who are refractory to their last line of therapy will be reported.

#### **4.5. Prior and Concomitant Medications**

Medications administered prior to the first dose date of study drug will be considered as prior medications. Concomitant medications are defined as those medications taken on or after the first dose date through 30 days after the last dose date.

Prior medications will be summarized on ITT analysis set by therapeutic class, pharmacologic class, and preferred term.

Concomitant medications will be summarized on safety analysis set by therapeutic class, pharmacologic class, and preferred term. Similar summaries will be provided for subjects who received concomitant growth factor support, systemic steroids, antiviral systemic use, and prophylactic antiviral medications during the study, respectively.

Pre-dose medications and post-dose medications will also be summarized by therapeutic class, pharmacologic class, and preferred term, respectively.

#### **4.6. Subsequent Anticancer Therapies**

The total number of subjects who received subsequent anticancer therapy for multiple myeloma will be reported for safety analysis set in each treatment group. A summary of subsequent anticancer therapy will be presented by therapeutic class, pharmacologic class and preferred term.

In addition, for subjects who received subsequent anticancer therapy for multiple myeloma, the best response to the first subsequent anticancer therapy will be summarized.

#### **4.7. Extent of Exposure**

Extent of exposure to study drug will be summarized and presented on safety analysis set.

Treatment duration and the total number of treatment cycles will be summarized descriptively. The number and percentage of subjects treated within each cycle will also be summarized by treatment group.

Treatment duration in months is derived as last non-zero daratumumab dosing date – first non-zero daratumumab dosing date + 1 and then divided by 365.25/12. The maximum number of treatment cycles for each subject is the largest cycle number in which a subject receives any non-zero dose of daratumumab.

In addition, duration of daratumumab administration in minutes is derived for each visit separately. It includes both interruption time and actual dose administration time, and is calculated as maximum dose administration end time – minimum dose administration start time. Duration of daratumumab administration in minutes will be summarized by first dose administration, second dose administration, and subsequent dose administrations.

Dose intensity, which is defined as the sum of total dose administered in all cycles divided by the number of treatment cycles, will be calculated and summarized for each treatment group. Dose intensity will be summarized for both treatment groups in both units of mg/cycle and mg/kg/cycle. Additionally, the daratumumab dose intensity will be summarized by Cycles 1-2, Cycles 3-6, and Cycle 7+ during the treatment.

Relative dose intensity (%), which is defined as the ratio of total dose received and total planned dose, will be calculated and summarized for each treatment group. Additionally, the relative dose intensity will be summarized by Cycles 1-2, Cycles 3-6, and Cycle 7+ during the treatment.

The incidences of treatment cycle delays, dose delays, dose skip and corresponding reasons will be provided. The frequencies of actions planned prior to infusion or injection start and taken during infusion or injection will be summarized, together with reasons reported on eCRF. In addition, a summary of treatment modifications will also be provided by Cycles 1-2, Cycles 3-6, and Cycle 7+ during the treatment.

A separate listing including all daratumumab dose administration data will be provided.

#### **4.8. Protocol Deviations**

Major protocol deviations will be summarized for ITT analysis set by the following types of deviation for each treatment group:

- Entered but did not satisfy criteria
- Developed withdrawal criteria but not withdrawn
- Received wrong treatment or incorrect dose
- Received a disallowed concomitant treatment
- Other

A list of subjects with major protocol deviations including subject ID, type of deviation, and reasons for deviation will be provided.

### **5. EFFICACY**

Assessment of disease will be conducted in accordance with the IMWG response criteria. Efficacy evaluations will include the following: measurements of myeloma proteins, bone marrow examinations, skeletal surveys and other imaging studies, and serum calcium corrected for albumin.

## 5.1. Analysis Specifications

### 5.1.1. Level of Significance

For the co-primary endpoint of ORR, the hypothesis tests will be based on one-sided test at significance level of  $\alpha=0.025$  to demonstrate the non-inferiority of Dara SC relative to Dara IV. If the non-inferiority of the Dara SC relative to Dara IV is claimed and the lower bound of the two-sided 95% CI of the relative risk is  $\geq 100\%$ , the superiority of Dara SC relative to Dara IV will be concluded.

For the co-primary endpoint of maximum  $C_{\text{trough}}$ , one-sided test at significance level of  $\alpha=0.05$  is selected to demonstrate the non-inferiority of Dara SC relative to Dara IV in terms of the maximum trough concentration.

Non-inferiority of Dara SC relative to Dara IV will be claimed only if both endpoints of ORR and maximum  $C_{\text{trough}}$  meet their criteria. Therefore, the overall type I error will be strictly controlled at level of  $\alpha=0.025$  (one-sided). In addition, since maximum  $C_{\text{trough}}$  is a pharmacokinetic endpoint, the conventional choice of  $\alpha=0.05$  (one-sided) is selected.

Once the non-inferiority null hypothesis is rejected for both the ORR and maximum  $C_{\text{trough}}$ , the following major secondary endpoints ordered below will be sequentially testing for superiority by utilizing a hierarchical procedure to control familywise Type I error rate at a two-sided significance level of 0.05. The major secondary endpoints will be sequentially tested in the following order:

- 1) Rate of infusion-related reactions
- 2) Progression-free survival
- 3) Rate of VGPR or better
- 4) Overall Survival

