1.2.1. Clinical Studies

1.2.1.1. Single-agent Studies

Preliminary data as of 30 Jun 2016 from 2 ongoing clinical studies (GEN501 and 54767414MMY2002 [hereafter referred to as MMY2002]) and 1 completed clinical study (54767414MMY1002 [hereafter referred to as MMY1002]) are summarized below. For further details and the most up-to-date information about single-agent studies, please refer to the Investigator's Brochure (IB Daratumumab¹⁰).

Dara-IV as monotherapy induces deep and durable responses in subjects with heavily pretreated multiple myeloma. Phase 2 Study MMY2002 and Phase 1/2 Study GEN501 Part 2 (Part 1 was the dose-escalation phase of this first-in-human study) are ongoing single-arm, open-label studies in which subjects with relapsed and refractory multiple myeloma are administered Dara-IV as monotherapy weekly for 8 weeks, every 2 weeks for an additional 16 weeks, and every 4 weeks thereafter until disease progression or unacceptable toxicity. One hundred forty-eight (148) subjects treated with Dara-IV 16 mg/kg monotherapy were included in a combined analysis of efficacy in Study GEN501 and Study MMY2002. The overall response rate (ORR) for the combined data set was 31.1% (95% confidence interval [CI], 23.7%-39.2%). Responses included 3 subjects with stringent complete response (sCR; 2.0%), 4 subjects with complete response (CR; 2.7%), 13 subjects with very good partial response (VGPR; 8.8%) and 26 subjects with partial response (PR; 17.6%). Within the individual studies, the ORR was 35.7% (95% CI, 21.6%-52.0%) in Study GEN501 and 29.2% (95% CI, 20.8%-38.9%) in Study MMY2002. After a median duration of follow-up of 20.7 months in Study MMY2002, the Kaplan-Meier based median OS was 20.1 months.

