11.2. Sample Size Determination

In a previous clinical study (MMY2002), of 106 subjects with relapsed or refractory multiple myeloma who had received at least 3 prior therapies and who were treated with Dara-IV 16 mg/kg, an ORR of 29.2% (95% CI: 20.8%, 38.9%) was observed. Non-inferiority of Dara-SC to Dara-IV in the current study is defined using a 60% retention of the lower bound (20.8%) of the 95% CI from Study MMY2002. With a planned 1:1 randomization, 480 subjects (n=240 in the Dara-SC group and n=240 in the Dara-IV group) will be needed to demonstrate non-inferiority with a power of 80% and a one-sided alpha=0.025, assuming that the true ORR is the same for both groups. The sample size calculation is based on the methodology for the non-inferiority test for non-unity null, as described by Farrington and Manning (1990).⁸

The study is also designed to establish non-inferiority of the co-primary pharmacokinetics endpoint, maximum C_{trough} , between Dara-SC and Dara-IV. Dara-SC will be considered non-inferior to Dara-IV if the lower bound of the 90% CI for the ratio of the geometric means of C_{trough} on Cycle 3 Day 1 is at least 80% (non-inferiority margin of 20%). A one-sided test is selected based on previous analyses that demonstrated a strong relationship between maximum C_{trough} and efficacy. However, there is no apparent relationship between drug exposure in the therapeutic dose range and adverse events of interest. With the planned 1:1 randomization,

480 subjects a one-sided $\alpha=0.05$, the power will be $>95\%$. This assumes a true ratio of the maximum C_{trough} of 1, a non-inferiority margin of at least 80% of the geometric mean ratio, and a coefficient of variation of 0.6.

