### 1.3. Statistical Hypotheses for Trial Objectives

The clinical and pharmacokinetic hypotheses are that the ORR and maximum  $C_{\text{trough}}$  for Dara SC 1800 mg are not inferior to the ORR and maximum  $C_{\text{trough}}$ , respectively, for Dara IV 16 mg/kg in subjects with multiple myeloma who have received at least 3 prior lines of therapy including a PI and an IMiD, or whose disease is refractory to both a PI and an IMiD. Both the null hypotheses for clinical and PK need to be rejected to declare non-inferiority.

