## 1.4. Non-inferiority Margins Justification

The clinical non-inferiority of Dara SC relative to Dara IV in the current study is defined using a 60% retention of ORR from previous clinical Study MMY2002, a study of 106 subjects with relapsed or refractory multiple myeloma who had received at least 3 prior therapies and who were treated with Dara IV 16 mg/kg, an ORR of 29.2% (95% CI: 20.8%, 38.9%) was observed. There is no established standard of care for the targeted population, and the recent approvals were based on single-arm studies with ORR as the primary endpoint.

The 60% retention will result in minimal loss of benefit in terms of observed ORR. For example, if the observed ORR for Dara IV is 30%, then an ORR of at least 25% needs to be observed for Dara SC. The clinical relevance of the 60% retention of ORR was justified based on the benefit/risk of Dara SC and a strong indication of similar efficacy from early efficacy and pharmacokinetics data. Subjects enrolled into MMY2002 had a median of 5 prior lines of therapy. Outcomes for this population of patients generally are measured in months. Due to prior therapies, these patients also tend to be more frail, with lower organ reserves, compared with subjects with newly diagnosed multiple myeloma. A shorter infusion time would reduce time spent in a healthcare setting and a lower incidence of IRRs could enable them to stay on therapy longer. In addition, in the daratumumab Study MMY1004 Part 1, the ORR was 38% for 45 subjects receiving Dara-MD 1800 mg, and the maximum  $C_{\text{trough}}$  was similar or higher compared to Dara IV, strongly suggesting similar efficacy with Dara SC.

For the co-primary endpoint of maximum  $C_{\text{trough}}$ , the non-inferiority of Dara SC relative to Dara IV is defined using a non-inferiority margin of at least 80% of the ratio of geometric mean (GM) of maximum  $C_{\text{trough}}$ . Since this is a PK endpoint, the selection of non-inferiority margin and the choice of alpha level follow the convention for bioequivalence studies.

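### SAP 5.1.1 misstates the overall type I error: the joint non-inferiority claim is bounded by one-sided 0.05, not 0.025, because maximum Ctrough is tested at 0.05

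*SAP*

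**What the plan says.** SAP 1.3 sets the decision rule: "Both the null hypotheses for clinical and PK need to be rejected to declare non-inferiority". SAP 1.3.1.1 and 5.1.1 test ORR at one-sided 0.025 against a relative-risk margin of 60%. SAP 1.3.1.2 and 5.1.1 test maximum Ctrough at one-sided 0.05, requiring the lower limit of the 90% CI for the geometric mean ratio to reach 80%.

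SAP 5.1.1 restates the both-must-succeed rule and then draws an inference: "the overall type I error will be strictly controlled at level of" one-sided 0.025. The next sentence says that, because maximum Ctrough "is a pharmacokinetic endpoint, the conventional choice of" one-sided 0.05 applies. SAP 1.4 gives the same reason, that "the choice of alpha level follow the convention for bioequivalence studies". Neither document says that the overall 0.025 is meant for the ORR test alone.

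**The concern.** Requiring both tests to succeed removes the need to split alpha. It does not bring the joint level down to the smaller of two unequal alphas. The claim is wrong if ORR is inferior, if Ctrough is inferior, or if both are. Where only Ctrough is inferior, a well-powered ORR test passes nearly every time, and the 0.05 Ctrough test is almost the only barrier to a false claim.

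The sentence states the error rate of the trial's main conclusion, and the design does not have that rate. SAP Amendment 1 lists regulator comments on the alpha level among its reasons for revising Sections 1.3 and 5, so the statement is likely to be relied on and carried into the study report.

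**Working it through.** **Inputs.** From Protocol 11.2: 240 per arm; ORR with a "power of 80% and a one-sided alpha=0.025"; Ctrough at one-sided 0.05, margin 0.80, CV 0.6. ORR margin: relative risk R = 0.60 (SAP 1.3.1.1). Dara-IV response rates from Protocol 1.2.1.1: 20.8% (MMY2002 lower confidence limit), 29.2% (MMY2002), 31.1% (combined data) and 35.7% (GEN501). Assumed: independent tests, and 240 per arm for both endpoints.

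**Step 1: the plan's design figures.** Let p1, p2 be the true SC and IV rates, and q1, q2 = q1/R the rates restricted to the null. The Farrington-Manning power at n per arm is

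Φ{[(p1 − R·p2) − 1.96·s0] / s1}, with s0² = [q1(1−q1) + R²q2(1−q2)]/n and s1² = [p1(1−p1) + R²p2(1−p2)]/n.

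At p1 = p2 = 0.208: q1 = 0.1535, q2 = 0.2559, s0 = 0.02876, s1 = 0.03055. Power = Φ[(0.0832 − 0.0564)/0.03055] = Φ(0.88) = 81.0%, against 80% stated. The required size is 234 per arm, against 240.

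For Ctrough, log-scale SD = √ln(1.36) = 0.5545 and SE = 0.5545·√(2/240) = 0.0506. Power ≈ Φ(ln 1.25/0.0506 − 1.645) = Φ(2.76) = 99.7%, against more than 95% stated. Both design figures reproduce.

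**Step 2: the level of the joint claim.** P(both pass) cannot exceed the smaller of the two pass probabilities.

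- ORR truly inferior: P(false claim) ≤ P(ORR passes) ≤ 0.025.
- Ctrough truly inferior: P(false claim) ≤ P(Ctrough passes) ≤ 0.05.

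Over the whole joint null the bound is max(0.025, 0.05) = **0.05**. The stated 0.025 does not reproduce.

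**Step 3: how near 0.05 it comes.** At a true Ctrough ratio of 0.80, the false-claim rate is 0.05 × ORR power:

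| True Dara-IV ORR | 20.8% | 29.2% | 31.1% | 35.7% |
|---|---|---|---|---|
| ORR power, true ratio 1.0 | 0.810 | 0.941 | 0.957 | 0.982 |
| False joint claim, ratio 1.0 | 4.1% | 4.7% | 4.8% | 4.9% |
| False joint claim, ratio 0.9 | 3.0% | 3.9% | 4.0% | 4.4% |
| False joint claim, ratio 0.8 | 1.6% | 2.3% | 2.5% | 2.8% |
| ORR ratio above which the rate exceeds 2.5% | 0.86 | 0.81 | 0.80 | 0.78 |

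Exact binomial enumeration of ORR power at ratio 1.0 gives 0.812, 0.942, 0.958 and 0.983. A simulation of 200,000 trials at 29.2% gives a joint rate of 4.6%. Correlation of 0.2 to 0.6 between the test statistics raises the 20.8% figure from 4.1% to between 4.5% and 5.0%.

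**Step 4: the other parts of the null.** With the ORR ratio at 0.60 and Ctrough ratio 1, the nominal rate is 0.025 × 0.9971 = 2.49%. The exact size of the Farrington-Manning test here is 2.57% to 2.62%, giving 2.56% to 2.61% jointly, so 0.025 is itself a nominal figure. With both endpoints at their margins and independent tests, the rate is 0.025 × 0.05 = 0.125%.

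**The case against.** The strongest reply is that this is a wording error without operational effect. Both component alphas are stated openly and consistently, and 5.1.1 puts 0.025, 0.05 and the joint rule side by side, so a careful reader can derive the bound. That is correct, and it limits the point to a stated figure.

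Second, the excess is narrow. The table fixes Ctrough exactly at its margin. With equal response rates and 240 per arm, the joint rate exceeds 2.5% only for true Ctrough ratios from about 0.79 to 0.80; at 0.75 the Ctrough error alone is about 0.18%. This also stands. The rate can be below 2.5% in many places where ORR is not inferior; what fails is the guarantee, which the SAP asserts as strict.

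Third, equal response rates at a Ctrough ratio of 0.80 may be unrealistic, since Protocol 11.2 cites "previous analyses that demonstrated a strong relationship between maximum" Ctrough and efficacy. The documents do not settle this. Protocol 3.2 links 274 µg/mL to 90% of the maximal effect on ORR and expects about 80% of Dara-IV subjects to reach it, so a 20% lower trough need not reduce ORR much. The 0.05 bound does not depend on the answer.

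Fourth, 0.025 might have been meant for ORR alone. The text calls it overall and derives it from the joint rule. If ORR alone was meant, the sentence still needs rewording.

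**Conclusion.** The sentence is wrong as written. The nominal one-sided type I error of the joint non-inferiority claim is at most 0.05, twice the stated 0.025. The 0.025 bound is guaranteed, nominally, only when ORR is truly inferior. The 0.05 bound follows from the decision rule and needs no assumption about response rates, correlation or the number of PK-evaluable subjects.

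The illustrative 4.1% to 4.9% rests on a true Ctrough ratio of exactly 0.80, equal response rates, 240 per arm for ORR and independent tests. The 2.49% and 2.56% to 2.61% figures also assume that all 240 per arm are PK-evaluable; the real number will be smaller by an amount the documents do not give.

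Testing Ctrough at 0.05 is not in error. Sample size, decision rules, analyses and error control for the secondary endpoints are unaffected.

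**What to change.** In SAP 5.1.1, replace the sentence on the overall type I error with:

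> ORR is tested at nominal one-sided 0.025 and maximum Ctrough at nominal one-sided 0.05; the overall nominal one-sided type I error of the joint non-inferiority claim is at most 0.05, and at most 0.025 (nominal) when ORR is truly inferior.

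The 90% CI criterion for Ctrough stays. The cost is one sentence and a less favourable stated figure; no new data or analysis is needed.

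The stated 0.025 would become nominally true only if Ctrough were also tested at one-sided 0.025. At 240 per arm that would lower Ctrough power from 99.7% to 99.3%, and by more if fewer subjects are PK-evaluable (to 94.9% at an assumed 160 per arm). That would change a justified criterion and is not needed to correct the text.
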